## 5.4 Study Flowchart

	PRE-TREATMENT VISIT	CYCLE 1 * DAY 17-21	CYCLE 1-4 DAY 13-17 	CYCLE 2-4  DAY 1 	END OF TREATMENT	FOLLOW UP 
Informed Consent	✓					
Medical History	✓					
ECOG Performance Status	✓			✓	✓	✓
Physical Exam & Vital Signs	✓			✓	✓	✓
PET-CT Scan	✓ 	✓ 			✓ 	
Contrast Enhanced CT – Chest, Abdo, Pelvis	✓ 					✓ 
Blood Sample – Future Research	✓ 					
GFR 	✓					
Full Blood Count	✓	✓	✓	✓	✓	✓
U&E's And LFT's	✓		✓	✓	✓	✓
AFP, hCG & LDH	✓		✓	✓	✓	✓
Testosterone, FSH and LH	✓				✓	✓ 
AE Reporting		To be reported from the start of the first treatment and within 30 days after the administration of the last dose of study drug				
Concomitant Medication		To be reported from the start of the first treatment and within 30 days after the administration of the last dose of study drug				

\*see appendix 3 for definitions

1. Glomerular filtration rate by EDTA clearance (a measured creatinine clearance using Cockcroft and Gault would be allowed if unable to perform EDTA clearance in adequate timeframe).
2. Within 28 days of beginning study treatment. *NB: If clinical decision was made a PET-CT scan can replace a CT scan at baseline (refer to section 5.3.1).*
3. To be performed up to 1 week after day 21 of cycle.
4. Patients who have a complete response to AUC-10 following cycle 1 will receive 2 further cycles. Those who do not achieve a complete response will have a further 3 cycles\*.
5. To be performed with 28 days of completing treatment. May be contrast enhanced CT if negative PET-CT scan on Day 17-21 of cycle 1.
6. Follow up to be carried out 2 monthly for 1st year and 4 monthly for 2nd year.

- 7. *CT scan to be performed in all patients who have a complete response to treatment (+/- surgery) at one and two year post therapy. For those patients requiring surgery following their treatment, a repeat CT scan must be carried out 2 months post end of treatment PET-CT scan and again at 2-3 months after the surgery has taken place (PET is not required for follow-up scans)\*.      Full blood count repeated to determine possible dose reductions also performed on Day 13-17.*
- 9. *± 3 day allowable window*
- 10. *Patients who have given consent for the storage of their samples (separate consent from the trial – will be indicated on registration form).*
- 11. *The hormone tests should be performed at baseline, end of treatment and annually at follow ups.*

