### **2.0 Study aims and objectives**

- To assess the safety, efficacy and toxicity of carboplatin AUC-10 in metastatic seminoma in a multi-centre setting.
- To see if, by using FDG PET-CT to assess metabolic response, the number of patients requiring 4 cycles can be reduced.

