## **3.0 Investigational plan**

### **3.1 Overall design**

This is a single arm phase II study to assess the safety, efficacy and toxicity of carboplatin AUC-10 in metastatic seminoma. Patients will be recruited from two sites.

Prior to the commencement of treatment, the patient should have a baseline PET-CT scan and a contrast enhanced CT scan performed within 28 days of study entry. Patients will be treated with carboplatin AUC-10 every 3 weeks (3 weeks=1 cycle) and on day 17-21 of the first cycle a repeat PET-CT scan will be performed. All PET-CT scans will be reviewed centrally and these results will determine how many further treatment cycles the patients will undergo. If the patient has a complete metabolic response [refer to Appendix 3], a further 2 cycles of carboplatin will be given, leading to a total of 3, and if the patient has not had a complete metabolic response but is responding, a further 3 cycles of carboplatin will be given [Refer to section 5.3.3 and page 20 (the table) for the timelines for the scans. Please refer to appendix 8 for the imaging protocol].

If no response is seen, then the patient will be taken off study and will receive conventional therapy using a cisplatin-based combination.

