**All PET CT scans will be performed at (or sent to) University College Hospital to be centrally reviewed.**

### **3.2 Treatment plan**

Carboplatin will be administered as a day case and doses will be calculated using the Calvert formula as below:

$$\text{Dose (mg)} = (\text{GFR} + 25) \times 10$$

Unless dictated by haematological toxicity, the Carboplatin dose should not be recalculated for each cycle. However, if the serum Creatinine has risen by > 20% above baseline, the Carboplatin dose must be recalculated using the Calvert formula with GFR determined by EDTA clearance. At the discretion of the PI an estimated creatinine clearance can be calculated using e.g. Cockcroft and Gault (or as per local policy) if the site is unable to obtain EDTA clearance.

Treatment will be repeated every 3 weeks (when platelets over  $100 \times 10^9/L$ , white blood count greater than  $3 \times 10^9/L$  or neutrophils greater than  $1 \times 10^9/L$ ).

If the blood count is below the level required to commence the next cycle of treatment (i.e. platelets less than  $100 \times 10^9/L$ , white blood count less than  $3 \times 10^9/L$  or neutrophils less than  $1 \times 10^9/L$ ) then a further blood count must be repeated 48 hours after the target treatment day. If the results of this repeat count show platelets greater than  $75 \times 10^9/L$  and rising, white blood count greater than  $3 \times 10^9/L$  or the neutrophils greater than  $1 \times 10^9/L$  the patient may commence to the next cycle [See Figure 1].

If neutrophils are less than  $1 \times 10^9/L$  and white blood count less than  $3 \times 10^9/L$ , filgrastim or lenograstim (GCSF) should be given for 2 days.

However, if the blood count remains below the level required it should continue to be monitored at 48 hour intervals until it has reached the required level for proceeding with further treatment (platelets are greater than  $75 \times 10^9/L$  and rising, white count greater than  $3 \times 10^9/L$  or the neutrophils are greater than  $1 \times 10^9/L$ ).

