**Please note that a delay of 14 days or more will require the patient to be withdrawn from study.**

**If a patient is admitted with neutropenic sepsis, prophylactic antibiotics e.g. ciprofloxacin, day 10 – 21 (with or without filgrastim or lenograstim) should be used for all subsequent cycles.**

If the platelet nadir (day 13 -17) is less than  $20 \times 10^9/L$ , then a **20% dose reduction** should be made on subsequent administration of carboplatin.

Patients will be required to attend hospital to receive Carboplatin as a day case.

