### 5.3.3 Central review of PET-CT scans

There are currently no well validated metabolic response criteria for PET-CT in seminoma. Hence, we will use the criteria for assessment of response developed for the evaluation of lymphoma [6].

A Complete Response will be defined as **complete resolution** of all previously seen sites of nodal and metastatic disease. If residual sites of metastatic disease persist then the PET-CT will be used to evaluate metabolic activity.

Metabolic Complete Remission will be defined as the level of FDG uptake within the lesion that is no greater than normal mediastinal uptake these patients will receive 3 cycles in total. Lesions with uptake greater than the mediastinum will be viewed as non-complete

responders. The PET data will be viewed on standardised SUV (standardised uptake value) setting of between 0 and 5.0 and a visual comparison will be made to assess the degree of uptake within abnormal tissue [7]. These criteria will have a high probability of distinguishing true complete responders from partial responders. Contrast enhanced CTs will be evaluated via the standard response criteria (Appendix 4).

All PET-CT scans will be centrally reviewed at University College London Hospital. The results from the report will be used to determine the number of further treatment cycle's patients will require, following cycle 1. Copies of locally reported scans (where relevant) should be sent to the central reviewer via the secure NHS Image Exchange Portal system (IEP) for review by the central reviewer (please refer to appendix 7). Sending images via IEP will not apply to sites where patients are scanned at UCLH, however, sites must ensure that the proforma is completed and sent to remind the central reviewer. In addition to sending images via the secure IEP system, sites must email a copy of the Proforma Request form (see Appendix 5 and 6) that is appropriate to each site) to the central reviewer to indicate that an image has been sent via IEP.

The central reviewer will review the image and return the generated report within the appropriate timelines as stated in the table below (see Appendix 7);

All scans for central review to be sent to;

[name]

Consultant in Nuclear Medicine

Institute of Nuclear Medicine, T5

University College Hospital

[name],

[name]

[contact]

Proforma Request form to be emailed to: [[contact]](mailto:[contact]) and  
[[contact]](mailto:[contact])

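### Flowchart footnote 3 lets the cycle 1 response PET-CT run to day 28, against day 17-21 elsewhere, without requiring it before the cycle 2 dose due on day 22

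*Protocol*

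**What the plan says.** Protocol 3.1 states that "on day 17-21 of the first cycle a repeat PET-CT scan will be performed". SAP 3.1 repeats this, and protocol 5.3.2 lists the scan for the same days. The flowchart in protocol 5.4 places it in a column for cycle 1, day 17-21, but footnote 3, attached to that cell, reads "To be performed up to 1 week after day 21 of cycle".

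On dosing, protocol 3.2 says "Treatment will be repeated every 3 weeks", subject to platelet, white cell and neutrophil thresholds. If the counts are too low, "a further blood count must be repeated 48 hours after the target treatment day", then every 48 hours until recovery. The limit is that "a delay of 14 days or more will require the patient to be withdrawn from study". The readable text of 3.2 sets no imaging condition for starting cycle 2.

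On use of the scan, protocol 5.3.3 says of the central review: "The results from the report will be used to determine the number of further treatment" cycles after cycle 1. A complete metabolic response leads to 3 cycles in total; a lesser response leads to 4. SAP 7.3.1 tabulates the response categories as the position after one cycle and has no rule for scans taken later.

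**The concern.** The body text and the footnote give different windows for the same scan. The wider one runs past the day on which the second dose is due, and no readable sentence puts the scan first. A site that follows the footnote could dose on day 22 and scan on day 26, and the image would then show response to two doses.

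Three things depend on this scan. It sets the number of cycles. If negative, it allows a contrast-enhanced CT to replace the end-of-treatment PET-CT (protocol 5.3.2 and flowchart footnote 5). It also supplies the metabolic response rate, which serves one of the two objectives in protocol 2.0: to see whether, "by using FDG PET-CT to assess metabolic response, the number of patients requiring 4 cycles can be reduced". If some scans follow a second dose, the SAP 7.3.1 table would combine response to one dose with response to two under a label that describes only the first, and nothing in that section would separate them.

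**Working it through.** The plan gives no calculation on this point, so the check is a count of days.

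**Inputs**
- First dose = day 1; cycle length = 21 days (protocol 3.1 and 3.2).
- Scan days in the body text: 17 to 21 (protocol 3.1 and 5.3.2, SAP 3.1).
- Scan limit in footnote 3: one week after day 21 (protocol 5.4).
- Repeat counts at 48-hour intervals after the target day; withdrawal at a delay of 14 days or more (protocol 3.2).

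**Dates**
- Nominal cycle 2 dose: 1 + 21 = day 22.
- Latest scan under footnote 3: 21 + 7 = day 28.
- Days added by the footnote: 22 to 28, which is 28 − 21 = 7 days.
- Latest cycle 2 dose without withdrawal: 22 + 13 = day 35.

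**Added scan days that fall strictly after dose 2**

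| Cycle 2 dose | Added scan days after dose 2 | Number of 7 |
|---|---|---|
| Day 22 (on time) | 23 to 28 | 6 |
| Day 24 (22 + 2) | 25 to 28 | 4 |
| Day 26 (22 + 4) | 27 to 28 | 2 |
| Day 28 (22 + 6) | none | 0 |

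The delayed rows assume that the dose is given on the day of the repeat count. From a delay of 6 days up to the maximum of 13 (dose on days 28 to 35), the footnote window closes no later than the day of dose 2, so no added day can fall after it. For shorter delays, or none, the outcome depends on which is done first. The table counts days on which the wrong order is possible; it does not say how often it happens. With the body-text window and dose 2 on day 22 or later, the number is 0.

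**Scale only.** One patient whose category differed would move the metabolic response rate by 1/45 = 2.2 percentage points with 45 patients, or 1/50 = 2.0 with 50. How many would differ is unknown.

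**Primary design.** The rule of at least 39 of 45 with rates of 75% and 90% reproduces: exact one-sided error is 0.0446 and power is 0.841. The timing of this scan does not enter that calculation.

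**The case against.** The strongest reply is that the order is already implied. Protocol 3.1 counts further cycles from a scan done in cycle 1, and protocol 5.3.3 speaks of cycles after cycle 1. Once dose 2 is given the patient is in cycle 2, so a scan at that point breaches the body text. The natural purpose of footnote 3 is to cover a patient whose cycle 2 is held for low counts, a case that protocol 3.2 describes at length. Protocol Figures 1 and 2 and SAP Figure 1 could not be read, and a treatment flowchart is where the order would normally appear. SAP 5.2.2 would list important deviations in any case.

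Much of this stands. A reader might infer that a scan on days 23 to 28 after dose 2 is fully compliant. The documents do not support that: it meets the footnote but conflicts with protocol 3.1 and 5.3.2 and SAP 3.1. A reader might also take "3 day allowable window" in flowchart footnote 9 as a dosing window and move dose 2 earlier or later. Protocol 5.3.2 attaches those days to the examination and blood tests on day 1 of cycles 2 to 4, and no text applies them clearly to the dose. Nor can one infer that a late scan is reported too late to choose between 3 and 4 cycles: a day 28 scan with the full 3-week review is reported by 28 + 21 = day 49, before cycle 4 is nominally due on 1 + 63 = day 64.

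What the reply does not remove is that footnote 3 is not limited to delayed cycles. Because one text permits the late scan and another does not, it is also unclear whether such a scan would be listed as an important deviation.

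**Conclusion.** The point holds as a conflict between a footnote and the body text, with a limited consequence. Under the footnote, and with cycle 2 given on time, 6 of the 7 added days allow a scan after two doses that would still direct treatment and be reported as response after one cycle. The extension is harmless whenever the scan precedes dose 2.

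This assumes 21-day cycles counted from the first dose, and that the unreadable figures do not already fix the order. The documents do not show how often late scans occur, or how far and in which direction they would shift the metabolic response rate, so no bias is claimed. The analysis concerned is descriptive and the primary endpoint is unaffected. It is a cheap improvement to consider.

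**What to change.** Reword footnote 3 along these lines: *day 17-21, or up to 1 week later if cycle 2 is delayed, and in all cases before the cycle 2 dose*. If the figures already show this order, the edit only brings the text into line with them.

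In SAP 7.3.1, keep all decision scans in the table, flag any acquired after the cycle 2 dose, and also report the after-one-cycle metabolic response rate restricted to scans before that dose. If recruitment has closed, this step still works alone. The dates should already be held, since SAP 3.4.1.1.1 derives progression-free survival from scan dates and SAP 6.5 summarises cycle lengths.

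The cost is one footnote edit, one derived variable (scan date minus cycle 2 dose date), one extra table row and slightly less scheduling flexibility for sites. The sample size does not change.

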## **5.5 *Follow up***

- Patients will be followed up as part of the study for 2 years following completion of treatment.
- Outpatient follow up visits will be carried out **2 monthly** in the first year and **4 monthly** in the second year. Patients will then be followed at the PI's discretion and/or standard care.
- Details of disease progression must be documented on the CRF.
- Any further therapy for metastatic seminoma must be documented on the CRF.

## **6.0 *Investigational Medicinal Product(s)/treatment details***

### **6.1 *Description of IMP***

**Carboplatin** is a platinum-containing anticancer agent much like cisplatin but is more toxic to the myeloid elements of bone marrow. However when used as a chemotherapy agent in solid tumours it produces less nausea, neurotoxicity, ototoxicity, and nephrotoxicity.

### **6.2 *Product sourcing manufacture and supply***

Carboplatin is a licensed product within the EU. Local pharmacies will source carboplatin from NHS commercial stock.

### **6.3 *Pre-Medication***

In the administration of prophylactic anti-emetics in conjunction with highly emetogenic chemotherapy (e.g. dexamethasone 16mg and a 5-HT3 antagonist pre carboplatin, dexamethasone 8mg/day for days 2 and 3 and metoclopramide 20mg 3x/day for days 1 to 5) centres should follow local practice.

### **6.4 *Prescription of IMP***

Prescriptions for carboplatin for this study should be in accordance with local policies and should be identifiable as being part of the clinical trial. The local PI or doctor on the delegation log will only be able to prescribe carboplatin.

## **6.5 Preparation and administration of IMP**

Carboplatin will be prepared by chemotherapy pharmacy departments and the dose calculated using the Calvert formula, as below:

$$\text{Dose (mg)} = (\text{GFR} + 25) \times 10$$

Unless dictated by haematological toxicity, the Carboplatin dose should not be recalculated for each cycle. However, if the serum Creatinine has risen by > 20% above baseline, the Carboplatin dose must be recalculated using the Calvert formula with GFR determined by EDTA clearance. At the discretion of the PI an estimated creatinine clearance can be calculated using e.g. Cockcroft and Gault (or as per local policy) if the site is unable to obtain EDTA clearance.

This dose should be administered in 500ml glucose 5% over 60 minutes, or as per institutional local practice.

Dose banding is not permitted; however, rounding of carboplatin dose to nearest 10 mg is acceptable.

## **6.6 Prior and concomitant therapies**

Concurrent therapy with nephrotoxic or ototoxic drugs such as aminoglycosides, vancomycin, capreomycin and diuretics, may increase or exacerbate toxicity due to carboplatin induced changes in renal clearance.

Combination therapy with other myelosuppressive agents may require dose changes or rescheduling of doses in order to minimise the additive myelosuppressive effects.

### **6.6.1 Recording concomitant medications**

Concomitant medications should be reported from the start of the first treatment and within 30 days after the administration of the last dose of study drug. As the IMP (Carboplatin) is a licensed product, there is no requirement to record concomitant medications administered as supportive care in the CRFs i.e. all anti-emetics, medications for indigestion, acid suppression, routine antibiotics for infection/ neutropenia and simple analgesics. However, concomitant medications are expected to be fully listed on all Serious Adverse Event forms should a safety event occur and reported to the sponsor within the appropriate timelines.

The concomitant medications which are not required to be reported on CRFs are listed on the next page.

**Fluids**  
0.9% NaCl  
5% Glucose  
Compound Sodium Lactate (Hartman's Solution)  
With or without additives e.g. KCl, MgSO4, Calcium

**Anti-emetics**

Domperidone  
Metoclopramide  
Cyclizine  
Levomepromazine  
Olanzapine  
Haloperidol  
Lorazepam  
Granisetron  
Ondansetron

Aprepitant

Dexamethasone  
Prednisolone

**Analgesics**

Aspirin  
Paracetamol  
Codeine  
Dihydrocodeine  
Tramadol  
  
Morphine  
Diamorphine  
Oxycodone  
Fentanyl  
  
Naproxen  
Ibuprofen  
Diclofenac

**Antibiotics**  
Co-amoxiclav  
Piperacillin/ Tazobactam  
Amoxicillin  
Benzylpenicillin  
Flucloxacillin

Cefuroxime  
Ceftriaxone  
Ceftazidime

Meropenem  
Imipenem

Gentamicin  
Amikacin  
Vancomycin  
Teicoplanin

Co-trimoxazole  
Doxycycline  
Tigecycline

Trimethoprim

Ciprofloxacin  
Levofloxacin

Clarithromycin

Itraconazole  
Fluconazole  
Caspofungin  
Amphotericin  
Micafungin  
Terbinafine

Aciclovir

**Acid Suppression**

Ranitidine  
Omeprazole  
Pantoprazole  
Lansoprazole

Gaviscon

Caphosol

**Anti-asthmatics**

Salbutamol  
Terbutaline  
Beclometasone  
Budesonide  
Formoterol

**Diuretics**

Bumetanide  
Furosemide  
Spironolactone  
Bendroflumethiazide

**Statins**

Simvastatin  
Pravastatin  
Atorvastatin

**Anti-hypertensives**

Atenolol  
Bisoprolol  
Metoprolol  
Ramipril  
Perindopril  
  
Lisinopril  
Enalapril  
Losartan  
Candasaratan  
Irbesartan  
Valsartan  
Lercanidipine  
Amlodipine  
Lacidipine  
Nifedioine  
Indapamide

**List of concomitant medications not required to be reported**

### **6.7 *Dose modification/reduction/delay***

If the patient has a nadir platelet count of  $<20 \times 10^9 /L$  then the dose of carboplatin should be reduced by 20%.

Please refer to figure 1 for guidance regarding dose delays.

### **6.8 *Toxicity profiles***

Please refer to the current SmPC toxicity and side effects information for carboplatin.

### **6.9 *Labelling/Packaging***

Labelling of the IMP will be undertaken by pharmacy staff, and will contain information to meet the applicable regulatory requirements of Annex 13.

### **6.10 *Blinding of IMP***

N/A

### **6.11 *Receipt of IMP supplies/Storage***

Carboplatin supplies will be sourced from NHS commercial stock therefore sites will be responsible for the ordering, receipt and storage of carboplatin. Storage will be in accordance with the current SmPC for carboplatin.

## **7.0 Pharmacovigilance**

### **7.1 General definitions**

#### **7.1.1 Adverse Event (AE)**

An adverse event (AE) is any untoward medical occurrence in a patient or clinical investigation subject who has been administered a medicinal product and which does not necessarily have a causal relationship with this treatment. An AE can therefore be any unfavourable and unintended sign (including an abnormal laboratory finding), symptom, or disease temporarily associated with the use of a medicinal (investigational or marketed) product, whether or not considered related to the medicinal product.

#### **7.1.2 Adverse Reaction (AR)**

An adverse reaction is any untoward or unintended response in a subject to an Investigational Medicinal Product (IMP), which is related to any dose administered to that subject. All adverse events judged by either the reporting investigator or the sponsor as having a reasonable causal relationship to a medicinal product qualify as adverse reactions. The expression reasonable causal relationship means to convey in general that there is evidence or argument to suggest a causal relationship.

#### **7.1.3 Serious Adverse Event (SAE) or Serious Adverse Reaction (SAR)**

A serious adverse event or reaction is any untoward medical occurrence at any dose that:

- Results in death
- Is life-threatening (defined as an event in which the patient or subject was at risk of death at the time of the event; it does not refer to an event which hypothetically might have caused death if it were more severe)
- Requires inpatient hospitalisation or prolongation of existing hospitalisation
- Results in persistent or significant disability/incapacity
- Is a congenital anomaly/birth defect
- Is an important medical event (defined as a medical event[s] that may not be immediately life-threatening or result in death or hospitalisation but may jeopardize the patient/subject or may require intervention (e.g., medical, surgical) to prevent one of the other serious outcomes listed in the definition above.) Examples of such events include, but are not limited to, intensive treatment in an emergency room or at home for allergic bronchospasm, blood dyscrasias, or convulsions that do not result in hospitalisation.

There is a distinction between the intensity (mild, moderate, or severe) and the seriousness of an adverse event. Thus, a severe reaction is not necessarily a SAE. For example, a headache may be severe in intensity, but would not be serious unless it met one of the previously listed criteria for SAEs.

